### 7.4.2. Safety Criteria for Adjustment or Stopping Doses

Enrollment in the study will be discontinued if the DMC determines that any of the following criteria have been met:

1. there is an increased risk of mortality due to brexanolone
2. there is an increased risk of ICU delirium due to brexanolone
3. there is an increased risk of prolonged intubation due to brexanolone
4. there is an increased risk of reintubation due to brexanolone

After each data review, the DMC may recommend that the study continue without modifications, continue with modifications, or be terminated, or that study treatment or enrollment is suspended. The DMC may also recommend stopping the study for futility at the time of interim analysis.

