**11.1.7. Data Collection at Follow-Up**

As applicable, the following will be documented during the follow-up visit(s):

- Dates and times of extubation and discontinuation of mechanical ventilation
  - The duration of time on mechanical ventilation will be calculated
- Dates and times of reintubation and re-initiation of mechanical ventilation
- Whether or not the participant requires oxygen delivered by high-flow nasal cannula (heated, humidified oxygen delivered via reinforced nasal cannula at flow rates >20L/min with fraction of delivered oxygen  $\geq 0.5$ ), and if so the date and time of initiation of oxygen delivery by high-flow nasal cannula
- Whether or not the participant requires noninvasive positive pressure ventilation and if so, the date and time of initiation of noninvasive positive pressure ventilation
- Whether or not the participant progressed to ECMO, and if so, the date and time of initiation and (as applicable) completion of ECMO
- Whether or not the participant progressed to tracheostomy, and if so, the date and time of the tracheostomy procedure
- Whether or not the participant died, and if so, the date, time, and cause of death

[REDACTED]

[REDACTED]

[REDACTED]

[REDACTED]

[REDACTED]

[REDACTED]

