### 12.2.3. Definition of Adverse Events of Special Interest (AESI)

An AESI is an AE/SAE of scientific and/or medical concern, specific to the product or program for which ongoing monitoring and rapid communication by the Investigator to the sponsor is required. Such AEs normally require thorough documentation and investigation in order to characterize them.

The following events are considered AESIs in this study:

- reintubation events
- delirium
- unplanned sedation/somnolence
- altered mental status
- sudden loss of consciousness

Such events should be reported on the AESI form to Sage or designee within 72 hours. If the AESI also qualifies as an SAE, an SAE form should be submitted per the guidelines per Section 12.2.6.

The investigator should provide additional details on the AESI form for the following AESIs as specified below:

- for reintubation events, include the reason for reintubation
- for delirium, document whether the participant had regained an appropriate state of orientation at some point after being extubated prior to onset of delirium

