#### 8.4.1. Adverse Events

Adverse events will be coded using Medical Dictionary for Regulatory Activities (MedDRA) Version 23.0 or higher. A treatment-emergent adverse event (TEAE) is defined as an adverse event with onset after the initiation of IP. The analysis of adverse events will be based on the concept of TEAEs.

If the date of an adverse event is incomplete and an unambiguous determination could not be made with respect to its onset time versus the first dose of IP and/or last dose of IP, the adverse event will be assumed to be a TEAE and a treatment period TEAE. For imputation of missing AE dates, please refer to Appendix A.

The incidence of all TEAEs and non-serious TEAE's will be separately summarized by SOC and preferred term PT. In addition, summaries will be provided by maximum severity (mild, moderate, severe, life-threatening, death) and by relationship (related, not related) to IP. Any TEAEs leading to discontinuation of treatment or withdrawal from the study and any treatment-emergent serious adverse events will also be summarized, sorted by descending frequency in SOC and PT.

For maximum severity, participants will be counted only once within each SOC and PT at the maximum severity in the following order: severe > moderate > mild; an AE with missing severity will be omitted from severity presentation. A participant will be counted only once within each SOC and PT at the strongest relationship to IP in the following order: related > not related. The incidences will be presented by descending frequency of SOC in the brexanolone group and then, within a SOC, by descending frequency of PT based on the participant count, and in alphabetical order of PT if the incidence within a PT is a tie.

The following table documents events considered to be AESI in this study, and the MedDRA preferred terms and lower-level terms (i.e., LLTs) in the right-hand column will be used to screen adverse events for possible AESI status. Where LLTs are specified, they take precedence in the determination of AESI's; when LLTs are left unspecified, it is understood that MedDRA preferred terms will take precedence:

AESI Term	MedDRA Preferred Term(s)
Loss of Consciousness	
 
1. Loss of consciousness
 
2. Altered state of consciousness
 
3. Syncope
 

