Excessive sedation	
 
1. Sedation
 
2. Somnolence
 
3. Sedation complication (note: this corresponds to the LLT of “Sedation excessive”)
 

Reintubation events	
 
1. Endotracheal intubation (note: this corresponds to the LLT of “Reintubate”)
 
2. Endotracheal intubation complication (note: this corresponds to the LLT of “endotracheal reintubation”)
 

Delirium	
 
1. Delirium
 
2. Intensive care unit delirium
 
3. Anesthetic complication neurological (note: this corresponds to the LLT of “Delirium on emergence”)
 

Altered mental status	
 
1. Mental status changes (note: this corresponds to the LLTs of “Acute mental status changes” and “Mental status changes”)
 
2. Mini mental status examination abnormal
 

The process for identification of AESI is to screen for MedDRA terms in the right-hand column and to query once any adverse events have been identified as meeting these broad criteria. AESI's will be tabulated separately from all TEAE's, using the same SOC x PT format.

All AEs, AESI and SAEs (including those with onset or worsening before the start of IP) through the end of the study will be listed. In addition, a listing containing individual participant's AE data for participants who died, and participants with SAEs leading to treatment discontinuation will be provided, separately.

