**APPENDIX D. PROCEDURAL TERMS USED IN THE IDENTIFICATION OF RESPIRATORY FAILURE AND UNSUCCESSFUL EXTUBATION**

Verbatim Procedural Term †	Interpretation Relative to Respiratory Failure	Interpretation Relative to Extubation
1. Bronchoscopy	No impact on determination of respiratory failure	No impact on determination of unsuccessful extubation
2. Chest Tube Insertion	No impact on determination of respiratory failure	No impact on determination of unsuccessful extubation
3. CPR	No impact on determination of respiratory failure	No impact on determination of unsuccessful extubation
4. ECMO	Respiratory failure	Extubation considered unsuccessful if within 48 hours of extubation
5. Initiation of Non-Invasive Positive Pressure Ventilation	Respiratory failure	Extubation considered unsuccessful if within 48 hours of extubation
6. Initiation of Oxygen Delivery by High-Flow Nasal Cannula	Respiratory failure	No impact on determination of unsuccessful extubation
7. Intubation	Respiratory failure	Extubation considered unsuccessful if within 48 hours of extubation

8. Intubation/ Brochoscopy/ Cauterization	Respiratory failure	Extubation considered unsuccessful if within 48 hours of extubation
9. Mechanical Ventilation	Respiratory failure	Extubation considered unsuccessful if within 48 hours of extubation
10. None: Extubated to 4L NC	Respiratory failure	No impact on determination of unsuccessful extubation
11. Pneumothorax, Right	No impact on determination of respiratory failure	No impact on determination of unsuccessful extubation
12. PS/CPAP	Respiratory failure	Extubation considered unsuccessful if within 48 hours of extubation
13. Reintubation	Respiratory failure	Extubation considered unsuccessful if within 48 hours of extubation
14. Tracheostomy	No impact on determination of respiratory failure	No impact on determination of unsuccessful extubation

†Mis-spellings present in the clinical database are displayed as-is in this table

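### SAP 8.4.1 identifies AESIs by a MedDRA term screen and does not mention the investigator's AESI form, so a form-reported AESI coded to an unlisted term can be missing from the AESI table

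*SAP*

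**What the plan says.** **Protocol.** Section 12.2.3 names five AESIs: reintubation, delirium, unplanned sedation or somnolence, altered mental status, and sudden loss of consciousness. They are described clinically, with no dictionary terms. The reporting route is a dedicated form: "Such events should be reported on the AESI form to Sage or designee within 72 hours". The form also takes the reason for a reintubation (12.2.3) and the suspected cause of an AESI judged unrelated to study drug (12.2.4). Section 13.6.1 commits to a summary of treatment-emergent AESIs and attaches no coding condition.

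**SAP.** Section 8.4.1 lists MedDRA terms which "will be used to screen adverse events for possible AESI status". On the level of coding it says "Where LLTs are specified, they take precedence in the determination of" AESIs. It then states the rule: "The process for identification of AESI is to screen for MedDRA terms in the right-hand column". The only further step is a query on each event that matched. AESIs are tabulated separately from all TEAEs, by system organ class and preferred term.

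**Other places where reintubation is recorded.** At follow-up, Protocol 11.1.7 collects "Dates and times of reintubation and re-initiation of mechanical ventilation". SAP 8.2.6 puts concomitant procedures on their own eCRF page and presents them as a listing. SAP Appendix D includes "13. Reintubation" among the verbatim procedure terms, for judging respiratory failure and unsuccessful extubation.

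**The concern.** The two documents start from different ends. The protocol starts from the investigator's clinical judgement, recorded on the form. The SAP starts from coded terms in the AE data. An event can satisfy the first and fail the second, and the SAP gives no instruction for that case.

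The AESI table is where these events are compared between arms under their own name. They are events that a sedating drug might plausibly cause. Two of them, reintubation and ICU delirium, are also among the four grounds in Protocol 7.4.2 on which enrolment would be stopped; one reads "there is an increased risk of reintubation due to brexanolone". Protocol 7.4.1 has the DMC receive AESIs on an ongoing basis. If that feed comes from the form, the final AESI table could disagree with it with no step in the plan to explain why.

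**Working it through.** No power, alpha or effect size enters this point, and the plan gives no figure to reproduce. The check compares the texts and traces individual records through the SAP rule.

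**1. Size of the screen.** Preferred terms counted from the table in SAP 8.4.1:

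| SAP category | Preferred terms |
|---|---|
| Loss of consciousness | 3 |
| Excessive sedation | 3 |
| Reintubation events | 2 |
| Delirium | 3 |
| Altered mental status | 2 |
| Total | 3 + 3 + 2 + 3 + 2 = 13 |

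Both reintubation terms carry a lower-level-term note, so the lower-level term decides for that category. Two SAP labels also differ from the protocol: excessive sedation against unplanned sedation/somnolence, and loss of consciousness without the protocol's qualifier that it be sudden.

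**2. What the query step can do.** Queries follow a hit. They can confirm or reject an event that the screen caught, but cannot recover one that it missed.

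**3. Tracing four kinds of record through the rule.**

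- *AESI on the form, AE coded to a listed term.* The screen finds it and it is tabulated as an AESI.
- *AESI on the form, AE coded to an unlisted term.* The screen does not find it. It is absent from the AESI table but present in the TEAE tables and the AE listing. For illustration, a site might report a reintubation on the form and word the AE as the condition that led to it.
- *Reintubation on the procedure or ventilation pages, with a matching AE coded to a listed term.* The screen finds the AE and nothing is lost.
- *Reintubation on those pages only.* The screen reads AE records, so it is not picked up. If it is on the procedure page, it appears in the procedure listing and can count under Appendix D.

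**4. Is another route given?** The visible text of SAP 8.4.1 mentions neither the AESI form nor an investigator flag, and it has no reconciliation with either. The visible parts of SAP 6.1 do not declare a change in how AESIs are identified; some of that section is redacted.

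**5. Size.** The number of affected events cannot be derived, and final enrolment is not given. The effect of one missed participant on one arm's incidence is 100/n percentage points, with n participants in the arm:

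- n = 50 (half of the planned 100): 100/50 = 2 points.
- n = 25: 100/25 = 4 points.

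Both values of n are assumptions. The second is the per-arm count that Protocol 13.8.1.1 set for an interim analysis which SAP 6.1.6 cancelled; it is not a known final count.

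**The case against.** The strongest defence is that the screen is a safety net. An AESI is by the protocol's own definition an AE or SAE, so a form-reported event should already be in the AE data. The SAP screens for possible status and then queries, which is how one would look for AESIs that sites failed to flag. Nothing in the SAP says that form-reported AESIs are removed. That reading is possible, and it is right that the gap rests on silence, not on an express exclusion. But the SAP calls the screen the process for identification, and no visible sentence adds the form reports. A programmer who followed the text would build the table from the screen alone.

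The second defence is that little is lost, because unmatched AEs stay in the TEAE tables and listings and procedures stay in their listing. This stands as a limit on the damage. It does not supply the comparison by AESI category: a listing does not compare arms, an unlisted preferred term in a TEAE table is not labelled as an AESI, and CAM-ICU results are only listed (SAP 8.4.7).

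Three stronger readings are tempting, and the documents do not support them.

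- *That reintubations are in fact missing.* Appendix D shows that the term occurs as a procedure. It does not show that the same event lacks an AE record, and the protocol requires one. A procedure-only reintubation would first be a lapse in site reporting. Redacted efficacy sections may also analyse reintubation from procedure data.
- *That DMC monitoring is compromised.* Protocol 7.4.1 gives the DMC AESIs directly, and the final SAP table does not feed the stopping criteria.
- *That the main safety comparison is undermined.* The safety endpoint named first in SAP 4.2 is the incidence of TEAEs, which this rule does not touch.

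**Conclusion.** The rule is wrong as written, and the fault is limited to the AESI table. It can leave out an AESI that the investigator reported on the form required by the protocol, solely because of how the event was coded, and the protocol's commitment to summarize AESIs carries no such condition. It would also not pick up a reintubation recorded only as a procedure or a ventilation date; whether any exists cannot be told from the documents.

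The conclusion assumes that the rule is applied literally and that no redacted text adds the form as a source. The number of events lost is unknown. At the assumed 50 or 25 participants per arm, each missed participant moves that arm's AESI incidence by 2 or 4 percentage points. TEAE tables, AE listings and the DMC's own supply of AESIs are not affected. The change should be made, but the validity of the trial does not depend on it.

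**What to change.** - In SAP 8.4.1, define the AESI set as every event reported on the AESI form, plus every screen hit confirmed on query. Tabulate it by the five categories of Protocol 12.2.3, using the protocol's labels.
- Before database lock, reconcile reintubation and re-initiation of ventilation records on the procedure and ventilation pages with the AE and AESI records. Send unmatched records to the site as queries and do not count them automatically: a procedure record has no investigator assessment as an AE, and some entries, such as the combined intubation and bronchoscopy item in Appendix D, may not be AESIs.
- Declare the change in SAP 6.1. If lock has already passed, SAP Section 2 requires that it be documented and discussed in the clinical study report.

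The cost is a few sentences in the SAP, one reconciliation listing and a few site queries. No new data collection is needed.

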#### 8.4.2. Concomitant Medications

Concomitant medications will be coded using WhoDD dictionary Global B3 September 2020 or later.

Concomitant medications are defined as those with a start date and time on or after the initiation of IP or those with a start date and time before the initiation of IP that are ongoing or with a stop date/time on or after the initiation of IP. If medication date/time is incomplete and it is not clear whether the medication was concomitant, it will be assumed concomitant. For imputation of missing concomitant medication dates, please refer to Appendix A.

A standard table of concomitant medications will be generated, showing both treatment groups as well as a total column, for the Safety Population. This table will show ATC Level 3 x Preferred Name and participants with multiple occurrences of a drug class or drug will be counted only once in the specific ATC classification or preferred name, respectively. Concomitant medications will also be listed.

Additionally, the following overlapping classes of medications will be separately tabulated using the same format as a standard concomitant medication table and will be restricted to the study days associated with ICU stay for each participant. Days in ICU occurring during any long-term safety follow-up will be included. For this purpose, medications of special interest are all qualifying medications with start dates that not only occur on or after the initiation of investigational product but also must occur during an ICU stay. There are no restrictions on medication stop date(s):

- CNS depressants (eg, benzodiazepines, opioids/opiates, barbiturates, propofol);
- other agents utilized for sedation effects (eg, dexmedetomidine);
- drugs administered to treat or prevent ICU delirium (eg, antipsychotics, atypical antipsychotics, or other agents intended for delirium treatment).

These classes of medications will be identified via the following ATC Level 3 codes:

- N01A (anesthetics, general)
- N02A (opioids)
- N03A (antiepileptics)
- N05A (antipsychotics)
- N05B (anxiolytics)
- N05C (hypnotics and sedatives)

A separate listing of these medications will be generated and will at minimum include dose, dose frequency, route of administration, and duration.

#### **8.4.3. Clinical Laboratory**

The clinical laboratory tests to be performed in this study are listed in [Table 4](#).

**Table 4: Summary of Clinical Laboratory Analytes**

Biochemistry	Renal Panel: glucose, calcium, phosphorus, blood urea nitrogen, creatinine, sodium, potassium, chloride, bicarbonate Hepatic Panel: albumin, alanine aminotransferase, aspartate aminotransferase, total bilirubin, direct bilirubin, indirect bilirubin, alkaline phosphatase, total protein, lactate dehydrogenase, gamma glutamyl transferase, c-reactive protein
Hematology	red blood cell count, hemoglobin, hematocrit, white blood cell count (i.e., leukocytes) with differential, platelet count, erythrocyte sedimentation rate
Coagulation	Activated partial thromboplastin time, prothrombin time, and international normalized ratio (INR)

For the laboratory results that is “ $<$  or  $= x$ ”, where  $x$  is a number as collected in the data, the numeric part of the result will be used in the calculation in the summary tables. The same is true if the result is presented as below limit of quantification (BLQ) and a lower limit of quantification (LLOQ) value is provided – LLOQ value will be used for calculation in the summary tables. The actual results as collected will be presented in the listings. The analysis summary will be performed for the scheduled laboratory values only. The unscheduled laboratory values will be presented in the listings.

All statistical analyses of laboratory values will be performed using SI units. Numerical values and change from baseline values will be summarized by actual treatment group at each windowed visit. If a normal range is provided for the parameter, the out-of-range values will be flagged as low or high, where applicable, in the participant data listings. Shift tables will also be generated.

The number and percentage of participants with potentially clinically significant (PCS) values will be provided in separate listings in hematology, serum chemistry, and liver function tests. PCS values will be identified for specific laboratory parameters as outlined in [Table 5](#). The summaries will be based on all post-baseline values, including both scheduled and unscheduled data. Percentages for PCS tables will be based on the number of subjects contributing observations.

Liver function tests will be monitored closely for PCS values, and will be summarized for occurrence any time post-baseline for the following parameters for these PCS threshold (for condition involving more than one parameter, the results need to be from the same timepoint):

Alanine Aminotransferase:  $>3 \times \text{ULN}$ ,

Aspartate Aminotransferase:  $>3 \times \text{ULN}$ , Alanine Aminotransferase or Aspartate

Aminotransferase:  $>3 \times \text{ULN}$ ,

Alkaline Phosphatase:  $>3 \times \text{ULN}$ ,

Total Bilirubin:  $>2 \times \text{ULN}$

Total Bilirubin  $>2 \times \text{ULN}$  **AND** (Alanine Aminotransferase or Aspartate Aminotransferase  $>3 \times \text{ULN}$ )

Total Bilirubin  $>2 \times \text{ULN}$  **AND** Alkaline Phosphatase  $>3 \times \text{ULN}$  **AND** (Alanine Aminotransferase or Aspartate Aminotransferase  $>3 \times \text{ULN}$ )

Any lab results considered clinically significant by the investigator will be captured as adverse events, hence will show up in AE listings and/or tabulations.

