**Duration of Treatment:**

Each participant will receive a single IV infusion of brexanolone or placebo for 60 hours.

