**12.1.6.2. Visit 2 (Hour 0) through Visit 9 (Day 7)**

Hematology and clinical chemistry panels are to be recorded daily; panels collected per standard of care may be used. Additionally, coagulation parameters should be recorded at the time points indicated in [Figure 1](#).

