**12.1.6.3. After Visit 9 (Day 8 through Day 28)**

Hematology and clinical chemistry panels are to be recorded on Day 14 and Day 28; panels collected per standard of care may be used. Additional hematology and clinical chemistry panels collected per standard of care between Day 8 and Day 28 should also be recorded.

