**Table 5: Potentially Clinically Significant Values for Specific Laboratory Parameters**

Laboratory Parameter	Units	Criteria for PCS Values (Observed values)	
		High	Low
Hemoglobin -male	g/L	>185	<115
Hemoglobin -female	g/L	>170	<100
Hematocrit-male	Fraction of 1	>0.55	<0.385
Hematocrit-female	Fraction of 1	>0.49	<0.345
Platelet count	10  /L	>600	<125
Leukocytes	10  /L	>15	<2.5
Basophils	10  /L	>0.5	NA
Eosinophils	10  /L	>1.5	NA
Neutrophils	10  /L	NA	<1.5
Lymphocytes	10  /L	>6.0	<0.5
Monocytes	10  /L	>1.4	NA
Albumin	g/L	>70	<28
Blood urea nitrogen	mmol/L	>10.71	NA
Calcium	mmol/L	>2.75	<2.0
Chloride	mmol/L	>120	<90
Creatinine	mmol/L	>3xULN or >3x Baseline	
Gamma Glutamyl Transferase	U/L	>3xULN	
Glucose	mmol/L	>13.9	<2.8
Sodium	mmol/L	>150	<132
Potassium	mmol/L	>5.4	<3.3
Protein	g/L		<45
Bicarbonate	mmol/L	>34	<18
Phosphorus	mmol/L	>1.94	<0.61
Liver Function Tests (LFT)			

Laboratory Parameter	Units	Criteria for PCS Values (Observed values)		
		High	Low	
Bilirubin	µmol/L	>2xULN		NA
Aspartate Aminotransferase	U/L	>3xULN		NA
Alanine Aminotransferase	U/L	>3xULN		NA
Alkaline Phosphatase	U/L	>3xULN		NA
Coagulation				
International Normalized Ratio (INR)	NA	>1.5x ULN		NA
Partial thromboplastin time (PTT)	sec	>1.5x ULN		NA

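### The laboratory PCS table in SAP 8.4.3 is not treatment-emergent, so baseline abnormality dilutes it and unequal inpatient sampling after Day 7 could tilt it

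*SAP*

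**What the plan says.** SAP 8.4.3 (Clinical Laboratory) defines the count in three places.

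- **Values used:** "The summaries will be based on all post-baseline values, including both scheduled and unscheduled data". For liver tests it adds that they "will be summarized for occurrence any time post-baseline".
- **Denominator:** "Percentages for PCS tables will be based on the number of subjects contributing observations". A PCS-free baseline is not required.
- **Criteria:** Table 5 is headed "Criteria for PCS Values (Observed values") and has no change-from-baseline column. The one criterion that refers to baseline is creatinine, ">3xULN or >3x Baseline". Because of the or, a participant above the first limit before infusion still counts.

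The exposure and sampling schedule come from the protocol.

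- **Duration of Treatment:** "Each participant will receive a single IV infusion of brexanolone or placebo for 60 hours".
- **Section 12.1.6.2, to Day 7:** "Hematology and clinical chemistry panels are to be recorded daily; panels collected per standard of care may be used".
- **Section 12.1.6.3, after Day 7:** panels on Day 14 and Day 28, and "Additional hematology and clinical chemistry panels collected per standard of care between Day 8 and Day 28 should also be recorded".
- **Figure 1 notes:** after hospital discharge only assessments possible by phone are done, which rules out blood draws.

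The same SAP section also plans change from baseline by windowed visit and shift tables. Table 3 places the shifts on the normal range.

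**The concern.** A reader will take a by-arm PCS percentage as the share of participants who developed a marked abnormality after starting treatment. This table mixes three groups: those who newly crossed a cut-off, those who were beyond it before infusion and stayed there, and those who crossed it weeks after a 60-hour infusion because they were still in hospital being tested.

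Eligibility does not prevent the second group. Of conditions that bear directly on these tests, Protocol 8.2 excludes only fulminant hepatic failure and end stage renal disease. The other laboratory displays do not separate the groups: the shifts use the normal range, and 8.4.3 limits the general summaries to scheduled values. Neither shows who newly crossed a PCS cut-off.

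At stake is the sensitivity of a safety table. A real laboratory signal could look small, or a gap could appear that reflects only how long each arm was sampled.

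**Working it through.** **The plan's own figure.** The plan states no PCS rate, so there is none to reproduce. Its only computed figure is the sample size: 50% versus 77%, two-sided 0.05, 80% power. The uncorrected two-proportion formula gives 49 per arm, 98 in total, which agrees with approximately 100. That figure is not in dispute; it supplies the planned 50 per arm and the two response rates used below.

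**Exposure.** 60 h / (28 × 24 h) = 60/672 = 8.9%. About 91% of the counting period falls after the infusion.

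**Dilution.** Let b be the share already beyond a cut-off at baseline (assumed still beyond it at some post-baseline draw) and p the new-onset rate among the rest. The table then shows b + (1 − b)p. Assume p = 30% and 15%, a true difference of 15 points and a risk ratio of 2.0.

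| b (assumed) | higher-rate arm | other arm | difference | ratio |
|---|---|---|---|---|
| 20% | 0.20 + 0.80 × 0.30 = 44% | 0.20 + 0.80 × 0.15 = 32% | 12 points | 1.38 |
| 40% | 0.40 + 0.60 × 0.30 = 58% | 0.40 + 0.60 × 0.15 = 49% | 9 points | 1.18 |
| 60% | 0.60 + 0.40 × 0.30 = 72% | 0.60 + 0.40 × 0.15 = 66% | 6 points | 1.09 |

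If p is equal in the two arms, b + (1 − b)p is equal too. Carry-over therefore produces no expected difference when there is no drug effect. It does add noise: with 50 per arm, the standard error of a chance difference in b is √(2b(1 − b)/50), which is 8.0 points at b = 20% and 9.8 points at b = 40% or 60%.

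**Unequal sampling.** Assume no drug effect on laboratory values and a daily risk h of a first PCS value from Day 8 while in hospital, with daily panels. A share d is discharged at Day 14 (7 days observed) and the rest are sampled to Day 28 (21 days). The expected PCS rate is d[1 − (1 − h)^7] + (1 − d)[1 − (1 − h)^21]. The documents give no discharge rates, so the planning response rates stand in for d: 50% placebo, 77% brexanolone.

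| h (assumed) | placebo | brexanolone | spurious difference |
|---|---|---|---|
| 1% | 12.9% | 9.6% | −3.3 points |
| 3% | 33.2% | 25.7% | −7.6 points |
| 5% | 48.1% | 38.4% | −9.7 points |

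If brexanolone delayed discharge, the sign would reverse. With equal stay and survival, the gap would be zero.

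**The case against.** The strongest reply is the randomized placebo arm, which follows the same counting rule. A reader might infer that the table cannot isolate a drug effect at all. The documents do not support that: under equal observation, baseline abnormality and late intensive-care events have the same expected frequency in both arms, so they weaken the comparison without biasing it. That part of the reply stands.

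The plan also has other routes to a laboratory signal. Change from baseline by visit addresses baseline level and separates infusion-period visits from later ones. Results that the investigator judges clinically significant become adverse events, and those are analyzed as treatment-emergent; Protocol 12.2.1 includes worsening of a pre-existing condition. A screen running to Day 28 matches the adverse event period and can catch delayed abnormalities. No hypothesis test on laboratory data is planned. All this lowers the weight of the point, but none of it shows who newly crossed a Table 5 cut-off.

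A reader might also want to replace the table with one limited to participants with a non-PCS baseline and to values through Visit 9. That would go too far. It would hide worsening from an abnormal baseline. The general Visit 9 window in SAP Table 2 runs from Day 6 to Day 10, so it is not a Day 7 cut. Coagulation has its own Visit 6 and Visit 9 windows (SAP 8.1.2), so the Day 28 argument does not apply to it.

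**Conclusion.** The point holds in a limited form. The PCS summary has no baseline exclusion and no end of window, and for hematology and chemistry it includes late draws that depend on staying in hospital. Baseline carry-over dilutes: under the assumed rates, a 15-point difference appears as 6 to 12 points. Unequal sampling can bias in either direction, by about 3 to 10 points in the assumed scenarios, provided that stay or survival differs by arm.

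Every rate here is an assumption; the documents give no baseline PCS prevalence, daily risk or panel counts. The sampling model ignores death, which also ends sampling. Abnormal values tend to persist, so repeated draws may add less than the formula suggests. Larger gaps follow if one assumes, say, 28 versus 18 panel days, but nothing in the documents supports a ten-day difference between arms.

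The study was stopped early (SAP 6.1) and the final number is not given. Fewer than 50 per arm would make chance baseline imbalance larger. This is a secondary, descriptive display, so the change is a cheap improvement.

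**What to change.** Keep the existing all-post-baseline PCS table and add a table to SAP 8.4.3 showing PCS at baseline (yes/no) by PCS post-baseline, per analyte, with high and low handled separately.

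- **Treatment-emergent PCS:** the numerator is participants with a non-missing, non-PCS baseline who meet the criterion in the period. The denominator is those with such a baseline and at least one value in the period.
- **Already PCS at baseline:** keep these participants in their own row with their worst post-baseline value, so that worsening stays visible.
- **Hematology and chemistry:** split into infusion start through Study Day 7, when daily panels are required, and Study Day 8 to 28. Write Study Day 7 rather than Visit 9. The reason for the cut is even sampling, not exposure: 60 of 168 hours, about 36%, is on infusion.
- **Coagulation:** use the SAP's own Visit 6 and Visit 9 windows.

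The split confines most of the unequal sampling to the later period. It does not remove the effect of early death or discharge. The cost is one extra table and smaller denominators per analyte, using data already collected.
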